### **8.3 Distinct Symptom clusters**

Participants selected for bio-sampling and who have agreed to be contacted to provide blood and saliva samples and use wearable devices (BioWear Sub-Study) will be contacted by a member of the research team to arrange a date and time for blood collection. Visits for blood and saliva sampling and collection of the wearable devices will take place at the NIHR/Wellcome Trust Clinical Research Facility (CRF) based at the Queen Elizabeth Hospital Birmingham at a time suitable for the participant. If for whatever reason participants are not able or willing to attend the CRF, home visits will be offered by a research nurse. Sample tubes will be pre-labelled with a unique anonymised global ID number, with no patient identifiable information and transported back to the CRF by the research nurse collecting the sample, in appropriate containment. Research staff conducting these visits will be members of the central research team and have consent, Good Clinical Practice (GCP), and phlebotomy training.

Participants selected for wearable monitoring will be provided with wearable devices (Garmin Vivosmart4) at the same visit that the bio-sampling is undertaken. The wearables will measure heart rate, oxygen saturation, step count and sleep quality. Via Atom5™ participants will be asked to undertake a 40-step test (they will be asked to walk 40 steps and measure their oxygen saturation pre and post-test, as well as logging activity on their app) once a week for each week that they use the wearable device. They will be asked to wear the device continuously (except for when the device requires charging) for 28 consecutive days from the time the device is first received, and then again for 28 consecutive days at six and 12 months. Participants will be provided with instructions and both online and telephone support in the use of the wearable devices. They will also be clearly informed that the devices will not be used to monitor their health and that their data will not be used to inform their care.

The data from the biosampling and wearables will be used in combination with symptom data from Atom5™ and clinical data from CPRD Aurum to deep phenotype Long COVID syndromes. The health service use (primary care consultations, prescriptions, A&E attendances and hospital admissions) and mortality of patients from each Long COVID syndrome will also be described using data from CPRD Aurum and linked data from Hospital Episode Statistics and Office for National Statistics mortality statistics (via CPRD).

### **8.4 Co-production workshops**

Participants will be invited to attend one or more of a series of co-production workshops that will be held either remotely or face-to-face. The aim of the workshops is to reach a consensus on which interventions should be recommended for use to treat Long COVID, which are suitable for evaluation in a clinical trial, and which should not be recommended, based on the available evidence. They will also be used to determine which of the agreed interventions are suitable for or could be adapted for remote delivery. Potential

## TLC Study

participants showing an interest will be provided with the relevant PIS, information on how to provide informed consent and event details. Participants will be asked to register prior to the event.

## 9.0 Data collection

### 9.1 Questionnaire data collection

Table 1.0-Summary of data collection

	Study time point												
	Baseline (BL)	1 M	2 M	3 M	4 M	5 M	6 M	7 M	8M	9 M	10 M	11 M	12 M
Consent	✓												
Confirmation of COVID-19 infection†	✓	✓	✓	✓	✓	✓	✓	✓	✓	✓	✓	✓	✓
Confirmation of hospital admission within 28 days of COVID-19‡	✓												
Name	✓												
Date of birth	✓												
Telephone number	✓												
e-mail address	✓												
Postal address	✓												
Sex at birth	✓												
Ethnic group	✓												
GP details	✓												
Height	✓												
Weight	✓												
Smoking status	✓												
Pregnancy status¥	✓												
SARS CoV-2 vaccination status	✓	✓	✓	✓	✓	✓	✓	✓	✓	✓	✓	✓	✓
Shielding status	✓												
Care home residence	✓												
Occupation	✓												
Occupational status	✓							✓					✓
Change in duration of working/education	✓												
Reason for change in working or education	✓												
Over-the-counter medication use	✓												

	Study time point												
	Baseline (BL)	1 M	2 M	3 M	4 M	5 M	6 M	7 M	8M	9 M	10 M	11 M	12 M
SBQ-LC™	✓	✓	✓	✓	✓	✓	✓	✓	✓	✓	✓	✓	✓
FACIT-Fatigue	✓	✓	✓	✓	✓	✓	✓	✓	✓	✓	✓	✓	✓
Modified MRC Dyspnoea Scale	✓	✓	✓	✓	✓	✓	✓	✓	✓	✓	✓	✓	✓
COVID-19 core outcome measure for recovery	✓	✓	✓	✓	✓	✓	✓	✓	✓	✓	✓	✓	✓
PHQ-2	✓	✓	✓	✓	✓	✓	✓	✓	✓	✓	✓	✓	✓
GAD-2	✓	✓	✓	✓	✓	✓	✓	✓	✓	✓	✓	✓	✓
PCL-2	✓	✓	✓	✓	✓	✓	✓	✓	✓	✓	✓	✓	✓
EQ-5D	✓	✓	✓	✓	✓	✓	✓	✓	✓	✓	✓	✓	✓
Bio-Sampling*					✓								
Garmin Wearable Device*					✓					✓			

† Only for controls

‡ Only for cases

¥ Only for females

\*Participants selected for bio-sampling and wearable Garmin devices. Data will be recorded from the Garmin devices at baseline (when the devices are provided) for 4 weeks, then 6 months and 12 months on.

Questionnaires will contain the unique Global ID and participant identifiable data (e.g. name, date of birth, address) will be stored separately from research data within the Atom5™ platform and will be accessible only to designated research staff for the purpose of contacting participants for research visits, registering participants at University Hospitals Birmingham for bio-sampling appointments, and where participants report severe Long COVID symptoms and may need advice or support.

Participants will complete the questionnaires monthly within a timeframe window of -/+ 7 days. Reminders/notifications will be sent by Atom5™ at Baseline/+2 days/+6 days for the baseline questionnaires and at -7 days/0/+2 days for subsequent ones.

At registration, all participants will be asked to provide the onboarding code provided in their invitation letter. Once participants have registered and provided informed consent, they will then be invited to provide baseline demographic data and report the presence of a wide range of symptoms, quality of life and work/education capability using validated tools via the Atom5™ platform.

Patient-reported outcomes will be assessed using symptom specific measures (Table 1): Symptom Burden Questionnaire-Long COVID (SBQ-LC™), FACIT-Fatigue, modified MRC Dyspnoea Scale, COVID-19 core outcome measure for recovery, Patient Health Questionnaire-2 (PHQ-2), Generalized Anxiety Disorder-2 (GAD-2), Abbreviated PTSD Checklist (PCL-2), and quality of life using the EuroQol-5D (EQ-5D).

The SBQ-LC™ will undergo further validation during the study. The development and initial validation of SBQ-LC™ has been applied for through a separate ethics application to the University of Birmingham Research Ethics Committee since participants will not be recruited via the NHS. The SBQ is a disease-specific, multi-domain instrument that will be used to assess symptom burden and functional status (interference). Respondents will be asked to indicate the presence of a symptom over the last 7 days and then provide an indication of symptom burden by providing a response on a 5-point ordinal scale measuring either symptom severity, symptom frequency, or interference. Higher scores will be indicative of greater symptom burden and interference.

The Functional Assessment of Chronic Illness Therapy –Fatigue Scale (FACIT-Fatigue) is a 13-item measure that assesses self-reported fatigue and its impact upon daily activities and function. It has been validated for use across a range of populations. The FACIT-Fatigue has a 7-day recall period and is scored on a 5-point Likert Scale from “0-Not at all” - to “4-Very much”. Individual items scores are summed (two items of which are reverse scored), multiplied by 13 and then divided by the number of items answered, with a higher score indicating less fatigue and better quality of life. It takes less than 5 min to complete.

The modified MRC Dyspnoea Scale is a modification to the widely used MRC Dyspnoea scale. The item has a 24-hour recall period and is scored on a 5-point Likert scale from “0 - I only get breathless with strenuous exercise” to “4 - I was breathless when dressing, talking or at rest”. It has a high degree of conceptual overlap with its parent clinical measure, the MRC Dyspnoea scale, which is in wide-scale clinical practice.

The COVID-19 core outcome measure for recovery is a single item intending to measure a return to the pre-illness state. The item has a same day recall period and is scored on a 5-point Likert scale from “0 - Completely recovered” to “5 - Not recovered at all”.

The Euroqol EQ-5D-5L comprises five items plus one visual analogue scale. It has been widely validated and used to assess health outcomes from a wide variety of interventions on a common scale for purposes of evaluation, allocation and monitoring. It is used by the National Institute for Health and Care Excellence (NICE) in health technology assessment. EQ-5D-5L takes only a few minutes to complete and has a same day recall period.

The GAD-2 is a screening tool for generalised anxiety disorder derived from the GAD-7. It comprises the first 2 items of the GAD-7, which are considered as the core anxiety symptoms (“feeling nervous, anxious or on edge”/Not being able to stop or control worrying”). The GAD-2 performs well as a screening tool for three other common anxiety disorders (panic disorder, social anxiety disorder, and PTSD). It has a recall period of two weeks. The GAD-2 has a global score (0-6, no weighting). A higher score indicates an increased likelihood of underlying anxiety disorder. The recommended cut-off score for further investigation is  $\geq 3$ . The GAD-2 has been validated in many studies and has retained the same psychometrics properties of the GAD-7 (86% sensitivity/83% specificity)

The PHQ-2 is a screening tool for depression derived from the PHQ-9. It comprises the first 2 items of the PHQ-9 (depressed mood and anhedonia). The PHQ-2 has a recall period of 2 weeks. It has a global score (0-6, no weighting). A higher score indicates an increased likelihood of an underlying depressive disorder. The recommended cut-off score for further investigation is  $\geq 3$ . The PHQ-2 has been validated in many studies and has shown a sensitivity of 83% and specificity of 92%.

The PCL-2 is an abbreviated version of the PTSD Checklist – Civilian version (PCL-C) and is used to screen for post-traumatic stress disorder (PTSD). It comprises two items (intrusive memories/distress associated with reminders of the traumatic event). It has a recall period of one month. An individual is considered to have

screened positive if the sum of these two items is  $\geq 4$  (Lang et al, 2005). Previous studies have shown that the PCL-2 has good psychometric properties and have shown sensitivity of .97 and specificity of .58.

The selection of appropriate patient-reported outcome measures has been informed by: i) outcomes that matter to patients identified through relevant literature, ii) input from the TLC lived experience advisory group, and iii) to align with outcomes being collected in HEAL-COVID. The team has included PRO measures that have demonstrated good psychometric properties in other clinical populations. The SBQ-LC™ will be validated in people with Long COVID in a separate study application.

Questionnaires will take approximately 15 minutes in total to complete. Completion will be permitted in all settings (home, care home, other). The order of administration will be standardised. Participants will be sent up to two reminders to help minimise missing data. For participants who are unable to use the Atom5™ app or website (due to patient preference, language, or other requirements) the research team will offer interview-led completion by telephone or video conference, with translators as required. Alternative language versions of each PRO will be provided when validated translations exist. All PROs will be used in accordance with user manuals when available. Where possible all data should be provided directly by the research participant. However, proxy completion by a carer, family member or friend will be permissible if the individual is too unwell or has technical difficulties. Proxy completion will be recorded on Atom5™.

Questionnaires will contain the unique Global ID and participant identifiable data (e.g., name, date of birth, address) will be stored separately from research data within the Atom5™ platform and will be accessible only to designated research staff for the purpose of contacting participants for research visits, registering participants at University Hospitals Birmingham for bio-sampling appointments, and where participants report severe Long COVID symptoms and may need advice or support.

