**STUDY SUMMARY**

Study Title	Therapies for Long COVID in non-hospitalised individuals: From symptoms, patient reported outcomes and immunology to targeted therapies (The TLC Study)
Short Title	Therapies for Long COVID in non-hospitalised individuals (TLC Study)
Study Design	Population based cohort
Study Participants	
Non-hospitalised individuals with a diagnosis of COVID-19 and symptoms lasting at least 12 weeks (“Long COVID”).
 
Matched control patients: i) individuals without a diagnosis of COVID-19; ii) individuals with a diagnosis of COVID-19 but without long-term symptoms.
 
Co-production workshops: Patients and their family members, healthcare professionals, experts in relevant symptoms and corresponding interventions, regulators, and policymakers (NICE).

Planned Size of Sample	
Minimum of 2000 individuals with a diagnosis of COVID-19.
 
Minimum of 500 individuals with Long COVID identified from the main cohort of individuals with COVID-19.
 
Minimum of 500 matched control patients without a diagnosis of COVID-19.
 
Minimum of 500 matched control patients with a diagnosis of COVID-19 but without long-term symptoms (i.e., without Long COVID).
 
Up to 200 individuals from the Long COVID cohort, 50 matched control patients without COVID-19, and 50 individuals with COVID-19 but without long-term symptoms, selected for bio-sampling (sample clusters) and wearables.
 
Co-production workshops: Approximately 40 stakeholders including patients and their family members, healthcare professionals, experts in relevant symptoms and corresponding interventions, regulators, and policymakers (NICE).

Follow-up duration	Monthly for 12 months
Planned Study Period	16 months
Research Question/Aim(s)	
To evaluate the symptom burden and underlying pathophysiology of Long COVID syndromes in non-hospitalised individuals.
 
To co-produce an intervention that can be delivered remotely for supporting individuals with Long COVID syndromes.
 
To gain consensus on therapies to recommend, therapies to evaluate and therapies to recommend against using for the clinical management of Long COVID.

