### 3.2 Research Objectives

1. To establish a representative population-based cohort of non-hospitalised individuals with COVID-19 and prolonged symptoms ("Long COVID").
2. To develop and validate a new patient-reported outcome (PRO) measure of symptom burden in individuals with Long COVID.
3. To collect validated PROs including symptoms, quality of life and work capability data longitudinally from the representative cohort of individuals with Long COVID using the Aparito Atom5™ platform.
4. To identify distinct symptom clusters ("syndromes") in non-hospitalised individuals with Long COVID and compare these Long COVID syndromes to known post-viral syndromes.
5. To measure immunological, proteomic and miRNA biomarkers to determine the underlying pathogenesis associated with Long COVID syndromes. To measure physical parameters via a wearable device to determine the physical exertions (heart rate intensity and movement) and sleep patterns observed in Long COVID syndromes.
6. To make recommendations on pharmacological and supportive therapies that: i) should be implemented without need for further evaluation; ii) should be evaluated in a clinical trial, and iii) should not be recommended for treating long COVID based on the available evidence.
7. Co-produce a supportive, remotely delivered intervention for individuals with long COVID, to address the symptoms associated with each Long COVID syndrome.
8. To evaluate patient and public involvement in the study.

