## 8.0 Study procedures

### 8.1 Population-based representative cohort of individuals with long COVID and matched controls

Eligible individuals who wish to participate will download the Aparito Atom5™ app or visit the website and register using their unique one-time use on-boarding code. They will then be asked to provide electronic consent on the app or website, which includes confirming that participants with a positive SARS CoV-2 RT-PCR result have not been hospitalised within 28 days of being diagnosed with COVID-19. Control participants will be asked if they have ever had COVID-19 to check eligibility for inclusion as a control subject. Once the consent form has been completed, participants will be asked to complete a brief demographic and clinical questionnaire. The questionnaire will ask for the following details: name, sex, date of birth, contact number, postal address, ethnic group, GP address, height, weight, smoking status, pregnancy status, SARS CoV-2 vaccination status, confinement (shielding) status, care home residence, occupation, occupational status (in work, furlough, etc.), and over-the-counter medications used to manage symptoms. Full details of these questions are provided in the appendix (Baseline data collection in Atom5™) and in Table 1.0.

Participants will then be invited to report the presence of established Long COVID symptoms and quality of life using validated tools at monthly intervals for a period of 12 months. At each time point, participants will be asked to confirm their willingness to continue to participate in the study. Those wishing to withdraw will be asked to complete a withdrawal form and advised that any data collected up to that point will need to be retained as it will have been used in aggregated data analyses.

As requested by our PPI group, we will ensure that people who are unable to use the app or website (due to no access to a smartphone or internet connection, patient preference, language, or other requirements) can participate through nurse interview-led appointments (telephone or video conference) with translators as required. Information and contact numbers will be provided on the PIS. Alternative language versions of each PRO will be provided where validated translations exist (see table below) The translated questionnaires are currently being programmed on the app.

	English	Bengali	Polish	Welsh	Punjabi	Gujarati	Urdu
EQ5D5L	X	X	X	X	X	X	X
FACIT F	X	X	X		X	X	X
PHQ-2	X	X	X		X	X	
GAD-2	X		X		X	X	X

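### Objective 3 promises longitudinal work capability data, but after baseline Table 1.0 repeats only occupational status; change in working time and its reason are asked once

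*Protocol*

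**What the plan says.** Objective 3 in section 3.2 reads, in part, "To collect validated PROs including symptoms, quality of life and work capability data longitudinally from the representative cohort of individuals with Long COVID". Work capability also appears in the rationale (2.0), in the outputs (4.0), in the WP1 description and among the stated uses of the digital platform (5.0). The Study Summary gives follow-up as "Monthly for 12 months".

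Table 1.0 in section 9.1 has three rows that bear on follow-up of work:

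- "Occupational status": ticked at baseline and at two later visits.
- "Change in duration of working/education": ticked at baseline only.
- "Reason for change in working or education": ticked at baseline only.

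Occupation is also recorded once, at baseline. None of these rows carries the footnote marks that restrict an item to cases or to controls.

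Section 8.1 describes the status item as "occupational status (in work, furlough, etc".) and refers to an appendix for full details. For the follow-up itself it says: "Participants will then be invited to report the presence of established Long COVID symptoms and quality of life using validated tools at monthly intervals". Work is not named there. The text after Table 1.0 in section 9.1 says that validated tools will cover work and education capability as well as symptoms and quality of life. It then lists eight measures: SBQ-LC, FACIT-Fatigue, modified MRC Dyspnoea Scale, the recovery item, PHQ-2, GAD-2, PCL-2 and EQ-5D.

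**The concern.** The objective and the schedule do not match. The protocol keeps change in working time and its reason as items separate from occupational status, which implies that they carry information that status does not. A participant who stays in work throughout but cuts hours, or regains them, need not change status category. A participant whose status does change may have done so because of illness, furlough or something else, and the item that would say which is not asked again.

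At stake is how far the study can describe the course of work capability in people with Long COVID, which is a named objective. Section 1.0 notes that symptoms may relapse and remit, so a single baseline report of working time is a weak guide to the following year. The schedule is fixed in this document, and analysis cannot supply data that were never collected. The linked records named in section 8.1 cover health service use and mortality, not working hours.

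**Working it through.** The protocol gives no sample size, power or error rate for work data, so there is no figure to reproduce. The check is a count of ticks in Table 1.0, followed by a reading of the text around it.

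**Time points.** Baseline plus 12 monthly assessments gives 1 + 12 = 13, of which 12 are follow-up.

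**Ticks per row.**

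| Row in Table 1.0 | All 13 points | 12 follow-up points |
|---|---|---|
| Change in working/education time | 1 | 1 − 1 = 0 |
| Reason for that change | 1 | 1 − 1 = 0 |
| Occupational status | 3 | 3 − 1 = 2 |
| Each of the eight patient-reported measures | 13 | 13 − 1 = 12 |

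By column position in the extracted text, the two later status ticks fall at months 7 and 12. The table was read by a program, so those months could be off by a column. The finding does not depend on them: the two change rows hold one tick each, and a column shift would not add another.

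**Is work time captured elsewhere in the schedule?** Section 8.1 names only symptoms and quality of life for the monthly reports. Section 9.1 describes the eight measures one by one: symptom burden and interference, fatigue, breathlessness, recovery, depression, anxiety, post-traumatic stress and general health status. None is presented as a measure of work or education capability. The promise of validated tools for that concept therefore has no named instrument behind it.

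**What remains visible after baseline.** Status at two visits shows moves into or out of work or furlough. It may show more, depending on response options held in an appendix that is not shown. Change in working time, and the participant's reason for it, are not recorded at any follow-up point.

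**The case against.** The strongest reply is that work is followed after baseline. Occupational status is repeated twice, with no restriction to cases or controls, so transitions can be described and compared between groups. The description of the item in section 8.1 is an open list. If the unseen options split full-time from part-time work, or include sick leave, some change in hours would register. SBQ-LC covers functional interference and FACIT-Fatigue covers the effect of fatigue on daily activities, and both are monthly. No passage defines work capability as hours plus reason. The analyses in section 10 and the sample size reasoning in section 14 do not use work data, so no analysis stated in this document fails.

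Most of this stands, and it limits the point. Three stronger readings are tempting, and the documents do not support them:

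- A reader might infer that reduced hours or partial return to work cannot be measured at all. The status response options are not shown, so that cannot be asserted.
- A reader might infer that Long COVID and control participants cannot be compared on work. Status is asked of everyone at the same visits. Moreover, the longitudinal promise in Objective 3 covers the Long COVID cohort. Sections 4.0 and 5.0 promise work-capability data for controls too, but do not say longitudinally.
- A reader might want a percentage of work changes missed. The documents give no rate of change in hours, and any assumed share of changes without a change of status would simply come back as the answer.

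The reply does not fill the gap itself. Whatever the status options are, the reason for a change is a separate item and is not asked again. The protocol does not present the monthly functional measures as work measures.

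**Conclusion.** The concern holds as a mismatch between a named objective and the data collection schedule. After baseline, occupational status is collected at 2 of 12 points, and change in working or education time and its reason at 0 of 12. A validated tool for work and education capability is promised but not named. The consequence is that the longitudinal picture will consist of status at two later visits, with at most a coarse signal on hours and no participant-reported reason for change.

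This rests on the tick counts in Table 1.0 and on the descriptions in sections 8.1 and 9.1. It assumes that the appendix questionnaires, which are not shown, do not add follow-up work items beyond those scheduled in Table 1.0. The point is worth acting on because the loss becomes permanent as each follow-up visit passes and the remedy is small. It does not undermine the cluster analysis or the SBQ-LC validation.

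**What to change.** In Table 1.0, tick both change items at each visit where occupational status is repeated, for all participants. That is 2 items × 2 visits = 4 added ticks. State the reference period in the item wording, for example since the last report, because a baseline question about change may refer to a different period. The cost is slightly more questionnaire burden at two visits, an app configuration change and a minor amendment.

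Repeating these items would not by itself meet the promise of validated tools, since nothing shown describes them as validated. Section 9.1 should either name the instrument meant or drop that word for work and education capability.

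If the two items are not repeated, there are two alternatives: add a named work-capability measure to the schedule, or narrow Objective 3 and the related outputs in sections 4.0 and 5.0 to occupational status. The last needs only a text change, but gives up follow-up information on working time and cause.

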#### Construct validity

A *priori* hypotheses will be generated to assess the SBQ-LC™’s construct validity. These hypotheses will be refined once the SBQ-LC™ scale structure, as a new PRO, is confirmed. Indicatively:

1. FACIT-Fatigue/– Scores on the FACIT-Fatigue will be positively correlated with SBQ-LC™ scores.
2. Modified MRC Dyspnoea Scale – Scores on the Modified MRC Dyspnoea Scale will be positively correlated with scores on the SBQ-LC™ .
3. Covid-19 core outcome measure for recovery – The Covid-19 core outcome measure for recovery scores will be negatively correlated with SBQ-LC™’s scale scores.
4. PHQ-2 – Scores on the PHQ-2 will be positively correlated with scores on the SBQ-LC™.
5. GAD-2 – Scores on the GAD-2 will be positively correlated with scores on the SBQ-LC™.
6. PCL-2 – Scores on the PLC-2 will be positively correlated with scores on the SBQ-LC™.
7. EQ5D-5L – Scores on the EQ5D VAS will be negatively correlated with scores on the SBQ-LC™.

For continuous scores, Pearson correlations will be used to examine associations. Interpretation of Pearson’s r-values will be based on the guidelines by Cohen (1988): small ( $r = 0.10$  to  $0.29$ ); medium ( $r = 0.30$  to  $0.49$ ); and large ( $r = 0.50$  to  $1.0$ ).

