#### Known-groups validity

Known-groups validity will be established by comparing SBQ-LC™ scores from individuals with Long COVID with matched controls. A hypothesis testing approach and parametric tests will be used to compare scores on the SBQ-LC™ between groups. A further sub-group analysis will be undertaken whereby Individuals with Long COVID will be grouped using their score rating on the Covid-19 recovery measure as an anchor question. Mean SBQ-LC™ scores will be compared across groups using parametric statistical tests.

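### The FACIT-Fatigue scoring rule fits its stated direction only under unshown item wording, that direction contradicts construct hypothesis 1, and the recovery item's range and hypothesis 3 do not fit its anchors

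*Protocol*

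**What the plan says.** Section 9.1 (Questionnaire data collection) says that FACIT-Fatigue "is a 13-item measure that assesses self-reported fatigue and its impact upon daily activities and function". Responses run from 0 (not at all) to 4 (very much). The scoring rule is "Individual items scores are summed (two items of which are reverse scored), multiplied by 13 and then divided by the number of items answered". The direction of the total is given in the same sentence: higher means less fatigue. For the SBQ-LC the same section states: "Higher scores will be indicative of greater symptom burden and interference".

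Section 10.2 (Construct validity) gives hypothesis 1 as "Scores on the FACIT-Fatigue will be positively correlated with SBQ-LC™ scores".

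Section 9.1 describes the COVID-19 recovery item as a 5-point scale. Its lowest anchor, 0, stands for complete recovery, and its highest, 5, for no recovery. Hypothesis 3 expects this item to correlate negatively with the SBQ-LC. Under Known-groups validity, participants with Long COVID are "grouped using their score rating on the Covid-19 recovery measure as an anchor question".

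Section 9.1 also says that all patient-reported instruments will be used according to their user manuals where these are available. The questionnaires are listed as an appendix (section 25.0), but their item texts are not in the document.

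**The concern.** On a scale that measures fatigue and its impact, one would expect most items to describe fatigue, so that answering very much means more fatigue. If 11 such items enter the sum unreversed, the total rises with fatigue, which is the opposite of the direction stated in the same sentence. An error of this kind is an exact reflection. Differences and correlations keep their size and only the sign changes, so nothing in the distribution need look abnormal.

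Table 1.0 schedules FACIT-Fatigue at baseline and at months 1 to 12, which is 13 time points. It also feeds the construct-validity hypotheses and, through them, the responsiveness testing. The recovery item is on the same schedule and supplies the grouping for one known-groups analysis. A validation that relies on hypotheses set in advance needs their signs to follow from the scoring.

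**Working it through.** **Inputs from the protocol.** 13 items; responses 0 to 4; two items reversed; sum × 13 / items answered; higher = less fatigue (all section 9.1). **Assumption, not in the protocol:** how the items are worded. Both ends of the range are shown.

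**Step 1: when rule and direction agree fully.** After scoring, every item must rise as fatigue falls. That requires the 11 unreversed items to be worded as absence of fatigue and the two reversed items to be worded as fatigue.

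**Step 2: 11 fatigue-worded items, two positively worded items reversed.** Let F be the raw sum of the 11 (0 to 44) and P the raw sum of the two (0 to 8).
- Rule as written: F + (8 − P)
- Score matching the stated direction: (44 − F) + P
- Sum of the two: 52, so the written rule gives 52 minus the intended score.
- Most fatigued respondent (F = 44, P = 0): 44 + 8 = 52 as written, against 0 + 0 = 0 intended.
- Least fatigued respondent (F = 0, P = 8): 0 as written, against 52 intended.
- With n items answered, the two prorated scores still add to (13/n) × 4n = 52, so missing items do not alter this.

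**Step 3: the opposite case, only the two reversed items fatigue-worded.** The written rule gives the most fatigued respondent 0 and the least fatigued 52. There is no conflict.

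**Step 4: between these ends.** Let k be the number of fatigue-worded items, with both reversed items of one kind.

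| Reversed items are | Most fatigued scores | Least fatigued scores | Direction at the extremes is wrong from |
|---|---|---|---|
| positively worded | 4(k + 2) | 52 − 4(k + 2) | k = 5 (28 against 24) |
| fatigue-worded | 4(k − 2) | 52 − 4(k − 2) | k = 9 (28 against 24) |

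**Step 5: hypothesis 1, with no assumption about items.** Higher FACIT-Fatigue = less fatigue; higher SBQ-LC = greater burden. If fatigue adds to burden, the expected correlation is negative. The protocol says positive. That sign is what the literal rule would give with fatigue-worded items, but it does not prove that they are so worded.

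**Step 6: recovery item.** The integers 0 to 5 are 0, 1, 2, 3, 4, 5: six values, not five. The modified MRC item in the same section is also called 5-point and runs from 0 to 4, which is five values. Since 5 means not recovered at all, a higher score should go with a higher SBQ-LC, so the expected sign is positive. Hypothesis 3 says negative.

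**Comparison.** For the modified MRC scale, PHQ-2, GAD-2 and PCL-2, higher scores are described as worse and the hypotheses are positive, so these agree. The sign mismatches are in hypotheses 1 and 3.

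**The case against.** The strongest case is that the protocol never shows an item, so an inversion cannot be proved from it. Section 9.1 gives a short description of an established instrument, not scoring code, and defers to user manuals. The phrase about two reversed items may only mean that two items are keyed opposite to the rest, with the next clause fixing the overall direction. The hypotheses are introduced as indicative and open to refinement. The recovery item's end labels and their order are clear, and the known-groups analysis compares mean SBQ-LC across response groups, so the numeric codes do not affect it.

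Much of this stands. A reader might infer that the study's fatigue scores will be inverted and that Long COVID will look better than controls. The documents do not support that. It needs mostly fatigue-worded items, literal implementation of the rule, and a manual that is absent or not followed.

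The rest does not dispose of the point. The manual clause is general and does not say that it overrides an explicit rule. The sentence nowhere says that the other 11 items are reversed. Refining the hypotheses once the SBQ-LC structure is confirmed would not change their signs, because section 10.2 itself requires greater burden to give higher SBQ-LC scores. The number of recovery groups still depends on whether there are five categories or six.

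**Conclusion.** The FACIT-Fatigue text cannot all be right. If the 11 unreversed items describe fatigue, rule and direction conflict, and the literal rule returns 52 minus the intended score (52 instead of 0 at worst). If they describe absence of fatigue, rule and direction agree. In both cases hypothesis 1 contradicts the stated direction. The 52-point reflection rests on the item-wording assumption; the contradiction with hypothesis 1 does not.

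For the recovery item, the count of six values against five and the sign of hypothesis 3 follow from the text alone. The text cannot show whether the point count or the end anchor is wrong. The effect on the known-groups analysis is small.

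This is a minor to moderate correction: a stated rule, a scale range and two hypothesis signs need reconciling. It is not evidence that any score has been or will be reversed.

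**What to change.** 1. Check the FACIT-Fatigue item wording against the questionnaire and the user manual.
2. Restate the rule in section 9.1 so that every fatigue-worded item is reversed (4 minus the response) and positively worded items are kept as answered, then summed, multiplied by 13 and divided by the items answered. The range is 0 to 52, with higher meaning less fatigue.
3. Make hypothesis 1 in section 10.2 negative to match.
4. Before data export, run one test record with the worst answer on every item through the Atom5 or analysis scoring. It should return 0.
5. In section 9.1, state the recovery item's codes as they appear in the app, use the same codes for the known-groups analysis, and align the sign of hypothesis 3 with them.

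The cost is a few sentences of protocol text and one scoring check, with no added burden for participants.
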